### **5.3.3 Dose Reductions**

Dose reductions may be allowed in the event that AEs are observed that are believed to be related to study drug, and which in consultation between the Investigator and the Medical Monitor, may be managed by a 50% reduction in dose. The duration of the dose reduction will be at the Investigator's discretion.

### **5.4 Treatment Compliance**

Treatment compliance will be documented in the eCRF by recording the date, time, and whether or not each IV dose of study drug was completely infused.

### **5.5 Prior and Concomitant Medication/Therapy**

Prior and concomitant medications include any drug (prescription or over-the-counter) or biological product (such as vaccines, blood or blood components) including herbal remedies or preparations. All prior/concomitant medications taken or received by a subject within the 28 days prior to the month 1 day 1 visit through the ETD/EOS visits, and any changes to concomitant medications during the study will be recorded on the appropriate eCRF.

#### **5.5.1 Allowed (Concomitant)**

- Calcium channel blockers (if on stable dose)
- Steroids (**exception:** not allowed for treatment of AL amyloidosis)

#### **5.5.2 Prohibited (Concomitant)**

- Chemotherapy
- Other investigational agents
- Myeloablative chemotherapy with ASCT
- Organ transplant
- Doxycycline
- Minocycline

- Diflunisal
- Histone deacetylase (HDAC) inhibitors

## 6 STUDY PROCEDURES

### 6.1 Evaluations by Visit

#### 6.1.1 Screening

With the exception of the assessments to be considered standard of care (e.g., blood and tissue samples), a signed ICF must be obtained before any study-specific screening evaluations are performed and should be documented in the subject's medical chart.

Screening evaluations and procedures will be performed within 28 days prior to the first study drug administration on month 1 day 1.

Rescreening is allowed once per subject.

The following will be performed within the 28 days prior to the month 1 day 1 visit:

- Signed ICF
- Review inclusion and exclusion criteria to assess eligibility
- Medical History - Obtain comprehensive cardiac, hematologic, and oncologic medical history; additionally, for all other conditions obtain relevant medical history for the past 5 years (including all major hospitalizations and surgeries), as well as the subject's current medical status
- Prior and concomitant medications/therapy
- Confirmation of diagnosis by prior immunohistochemical or mass spectrometry tissue typing of amyloid
- Complete physical examination including height, weight, and examination of general appearance; head, ears, eyes, nose, and throat; neck; skin; cardiovascular system; respiratory system; gastrointestinal system; and nervous system. The following should be assessed: macroglossia, submandibular nodes/fullness, adenopathy, echymoses, liver/spleen size (palpable +/-), ascites (+/-), and edema (which should be quantified on a scale of 0-4+).
- Vital signs – heart rate (HR), BP, respiratory rate (RR), and body temperature after the subject has been at rest for 25 minutes
- ECOG PS
- NYHA Class
- Hematology and chemistry (including amylase)
- Coagulation
- Troponin T or I
- NT-proBNP
- BNP
- Serum pregnancy test for WOCBP within 28 days before month 1 day 1 study drug administration. Note:

Women with tubal ligations are considered to be of childbearing potential but women who are surgically sterile (hysterectomy) or postmenopausal 22 years are not considered to be of childbearing potential

- Serum free light chains
- Serum protein electrophoresis (SPEP) and 24-hour urine protein electrophoresis (UPEP)
- Serum immunofixation electrophoresis (SIFE) and urine immunofixation electrophoresis (UIFE)
- Urinalysis - dipstick
- 24-hour urine protein and creatinine excretion
- Echocardiogram
- Electrocardiogram
- Archived urine sample
- Renal function studies
- Renal biopsy
- Inflammatory biomarkers
- Tryptase
- SF-36

### **6.1.2 Treatment Visits**

Study visits will occur every 28 days based on scheduling from month 1 day 1. A  $\pm$ 5-day window is allowed for visits starting after month 1. Subjects may receive up to 12 infusions of study drug; a minimum of 21 days between doses is required.

The predose assessments for each visit may be performed within the 2 days before the visit (with the exception of pregnancy tests, which must be performed within 24 hours of study drug administration). Local laboratory assessments will be performed.

Subjects who present with symptomatic orthostatic hypotension and/or systolic BP <85 mm Hg, which in the medical judgment of the Investigator would interfere with the subject's ability to safely receive treatment, will have study drug withheld. If study drug is withheld and subsequently rescheduled, laboratory assessments required for that visit will need to be repeated if they were drawn  $>$ 7 days prior to the rescheduled dosing date. However, a symptom-directed physical exam and vital signs need to be repeated prior to each dosing.

#### **6.1.2.1 Month 1 day 1**

Prior to Study Drug Infusion:

The following assessments will be done prior to dosing on month 1 day 1:

- Concomitant medications/therapies
- Assessment of AEs
- Directed physical examination - including weight and examination of the following: general appearance; head, ears, eyes, nose, and throat; neck; skin; cardiovascular system; respiratory system; gastrointestinal system; and nervous system. The components of the physical exam will be as clinically indicated; however, the following should be assessed: macroglossia, submandibular nodes/fullness, adenopathy, ecchymoses,

liver/spleen size (palpable +/-), ascites (+/-), and edema (which should be quantified on a scale of 0-4+).

- Vital signs including HR, BP, RR, and body temperature within 30 minutes before dosing, after subject has been at rest 25 minutes; assess in same position for all time points
- ECOG PS
- NYHA Class
- Hematology and chemistry laboratory testing (including amylase)
- NT-proBNP
- BNP
- Serum pregnancy test within 24 hours before study drug administration
- Urinalysis - dipstick
- Randomization – After the subject is randomized, study drug treatment may be initiated

### **Study Drug Administration:**

Subjects with symptomatic orthostatic hypotension and/or systolic BP <85 mmHg, which in the medical judgment of the Investigator would interfere with subject's ability to safely receive treatment, will have study drug withheld.

- Administer study drug IV over 120 ( $\pm 10$ ) minutes
- Vital signs including HR, BP, RR, and body temperature – assess 60 ( $\pm 10$ ) minutes after the start of the infusion; assess in same position for all time points

### **Assessments After Infusion:**

- Monitor subjects for 90 ( $\pm 10$ ) minutes following completion of the study drug infusion. The Investigator may increase this standard monitoring time if deemed appropriate or per local standards. In the event of any clinical concerns or suspicious signs or symptoms after the infusion, the subject will remain under observation for as long as the Investigator deems it appropriate.
- Vital signs including HR, BP, RR, and body temperature after subject has been at rest 25 minutes; assess in same position for all time points:
  - At the end of infusion (EOI) (+5 minutes)
  - 30 ( $\pm 5$ ) minutes after EOI
- Discharge subject from clinic if no immediate safety concerns and/or hypersensitivities are present after the post-dose assessments and monitoring period. In the event of any clinical concerns or suspicious signs or symptoms after the infusion, the subject will remain with the Investigator and study staff for further observation until the Investigator deems the subject can safely leave the clinic.

#### **6.1.2.2 Months 2 through 12 – day 1 ( $\pm 5$ Days)**

Prior to Study Drug Infusion:

The following assessments will be done prior to dosing on Day 1:

- Concomitant medications/therapies
- Assessment of AEs
- Directed physical examination -including weight and examination of the following: general appearance; head, ears, eyes, nose, and throat; neck; skin; cardiovascular system; respiratory system; gastrointestinal system; and nervous system. The components of the physical exam will be as clinically indicated; however, the following should be assessed: macroglossia, submandibular nodes/fullness, adenopathy, ecchymoses,

liver/spleen size (palpable +/-), ascites (+/-), and edema (which should be quantified on a scale of 0-4+).

- Vital signs including HR, BP, RR, and body temperature within 30 minutes before dosing, after subject has been at rest 25 minutes; assess in same position for all time points
- ECOG PS/NYHA Class
- Hematology and chemistry laboratory testing (including amylase)
- Coagulation
- Troponin T or I – Months 3, 6, 9, 12
- NT-proBNP
- BNP
- Serum pregnancy test (WOCBP)
- Serum free light chains – Months 3, 6, 9, 12
- SPEP and 24-hour UPEP – Months 3, 6, 9, 12
- SIFE and UIFE – Months 3, 6, 9, 12
- Urinalysis - dipstick – Months 3, 6, 9, 12
- 24-hour collection for urine protein excretion – Months 3, 6, 9, 12
- Inflammatory biomarkers – Months 3, 6, 9, 12
- SF36 – Months 3, 6, 9, 12

#### **Study Drug Administration:**

Subjects with symptomatic orthostatic hypotension and/or systolic BP <85 mmHg, which in the medical judgment of the Investigator would interfere with subject's ability to safely receive treatment, will have study drug withheld.

- Administer study drug IV over 60 ( $\pm 10$ ) minutes if the month 1 day 1 infusion was well tolerated.

#### **Assessments After Infusion:**

- Monitor subjects for 90 ( $\pm 10$ ) minutes following completion of the study drug infusion. The Investigator may increase this standard monitoring time if deemed appropriate or per local standards. In the event of any clinical concerns or suspicious signs or symptoms after the infusion, the subject will remain under observation for as long as the Investigator deems it appropriate.
- Vital signs including HR, BP, RR, and body temperature – after subject has been at rest 25 minutes; assess in same position for all time points:
  - 60 ( $\pm 10$ ) minutes after EOI

Discharge subject from clinic if no immediate safety concerns and/or hypersensitivities are present after the post dose assessments and monitoring period. In the event of any clinical concerns or suspicious signs or symptoms after the infusion, the subject will remain with the Investigator and study staff for further observation until the Investigator deems the subject can safely leave the clinic.

#### **6.2 Early Treatment Discontinuation (ETD) or Initial EOS visit: 30 ( $\pm 5$ ) days AFTER Final Dose**

A final visit should occur 30 ( $\pm 5$ ) days after the final administration of study drug. The assessments shown for ETD or initial EOS visit should also be conducted for any unscheduled visit (i.e. a visit not specified by the protocol) as clinically indicated or if deemed necessary.

- Concomitant medications/therapy
- Assessment of AEs
- Complete physical examination -including weight and examination of general appearance; head, ears, eyes,

nose, and throat; neck; skin; cardiovascular system; respiratory system; gastrointestinal system; and nervous system. The following should be assessed: macroglossia, submandibular nodes/fullness, adenopathy, ecchymoses, liver/spleen size (palpable +/-), ascites (+/-), and edema (which should be quantified on a scale of 0-4+).

- Vital signs including HR, BP, RR, and body temperature - after subject has been at rest 25 minutes
- ECOG PS
- NYHA Class
- Hematology and chemistry laboratory testing (including amylase)
- Coagulation
- Troponin T or I
- NT-proBNP
- BNP
- Serum pregnancy test (WOCBP only)
- Serum free light chains
- SPEP and 24-hour UPEP
- SIFE and UIFE
- Urinalysis -dipstick
- 24-hour urine protein excretion
- Inflammatory biomarkers
- SF36

#### **6.2.1 Confirmatory EOS visit: 30 (+/- 5) days after the initial EOS visit**

A confirmatory EOS visit should occur 30 ( $\pm 5$ ) days after the initial EOS visit. final administration of study drug. The assessments include.

- Concomitant medications/therapy
- Assessment of AEs
- Complete physical examination -including weight and examination of general appearance; head, ears, eyes, nose, and throat; neck; skin; cardiovascular system; respiratory system; gastrointestinal system; and nervous system. The following should be assessed: macroglossia, submandibular nodes/fullness, adenopathy, ecchymoses, liver/spleen size (palpable +/-), ascites (+/-), and edema (which should be quantified on a scale of 0-4+).
- Vital signs including HR, BP, RR, and body temperature - after subject has been at rest 25 minutes
- ECOG PS
- NYHA Class
- Hematology and chemistry laboratory testing (including amylase)

- Coagulation
- Troponin T or I
- NT-proBNP
- BNP
- Serum pregnancy test (WOCBP only)
- Urinalysis -dipstick
- 24-hour urine protein excretion
- SF36

### **6.3 90-day Post-dose Pregnancy Test**

For WOCBP only: Obtain a local laboratory serum pregnancy test 90 ( $\pm 5$ ) days after the last administration of study drug.

### **6.4 Vital Status Follow-Up Phone Call**

Conduct vital status telephone call approximately 4 weeks after ETD visit or confirmatory EOS visit and approximately every 3 months thereafter until 24 months after study entry if the subject does not comply with standard-of-care visits or testing.

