Estimated Study and Treatment Duration	
Each subject's study duration may be up to 26 months, consisting of a Screening Phase (1 month), a Treatment and Assessment Phase (13 months) that includes 12 months of treatment, the initial end-of-study (EOS) Visit 30 (<math>\pm 5</math>) days after the last dose and the confirmatory EOS visit 1 month later, and the Open-label Extension (OLE) Phase during which subjects will receive active treatment with NEOD001 for 12 months and may receive concurrent chemotherapy.
 
The 13 month Treatment and Assessment Phase is the active study period.
 
During the OLE study, subjects will be seen monthly, and local laboratory testing for the OLE study will be obtained and collected every 3 months.

Subject Eligibility Criteria	
Inclusion Criteria (subjects must meet all of the following criteria):
 
 
1. 18 years of age or older.
 
2. Biopsy-proven diagnosis of AL amyloidosis by immunohistochemistry or mass spectroscopy of a tissue biopsy excluding bone marrow.
 
3. Screening renal biopsy for RAIN confirming AL amyloidosis as exclusive or dominant cause of renal damage
 
4. Persistent renal involvement from diagnosis with proteinuria (predominantly albumin) <math>> 500\text{mg/day}</math> in a 24-hour urine collection
 
5. CKD 1 to 3 (eGFR <math>\geq 30</math>)
 
6. <math>\geq 1</math> prior systemic hematologic therapy for a free light chain (FLC) producing hematologic malignancy underlying the initial diagnosis of AL amyloidosis with at least a partial FLC response (PR, VGPR, CR) to treatment deemed
 

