The primary endpoint is the confirmed renal response rate at 13 months after initiating therapy (after 12 months of NEOD001 or placebo). Renal response is measured according to criteria that have been developed and validated in two large European cohorts, employing eGFR and 24-hour proteinuria. A renal response is a  $\geq 30\%$  decrease in proteinuria or drop of proteinuria below 0.5 g/24h in the absence of renal progression. Renal progression is defined as  $\geq 25\%$  decrease in eGFR. A confirmed renal response is one that has been documented as present at both 12 and 13 months after initiating therapy. Secondary end-points of this trial involve comparisons of measured GFR (mGFR) compared to eGFR at study entry, and comparisons of patients who receive NEOD001 or placebo with respect to time to CKD 4 or 5 status, time to eGFR  $\leq 15$  or dialysis, time to doubling of serum creatinine, time to a  $\geq 40\%$  reduction in eGFR, and rates of renal response and progression at 26 months after study entry in patients with maintained hematologic responses. We will also assess safety and tolerability of NEOD001 and mortality due to all causes at 26 months.

In this multicenter trial, we plan to treat AL patients who are greater than 18 years old and have had hematologic responses to their last prior therapy and who have persistent AL renal involvement with renal stage 1, 2 or 3 disease. Patients must be chronic kidney disease stage (CKD)  $\leq 3$ . Patients with NT-proBNP  $\geq 1800$  are not eligible for this trial. Patients must have prior confirmed AL amyloidosis based on Congo red and immunohistochemical staining or mass spectrometry typing of a tissue biopsy (excluding bone marrow), and patients screened and found otherwise eligible must have a screening renal biopsy to confirm that amyloidosis is the cause of renal disease before being declared eligible for RAIN. Eligible patients are then stratified based on response to prior therapy (CR/VGPR vs PR) and renal stage (stages 1 or 2 vs stage 3) and randomized.

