#### **3.2.2 Secondary Endpoints**

- Measured GFR at study entry (Appendix 9)
- Measured during and at the end of the active study period:
  - Time to CKD 4 or 5
  - Time to eGFR < 15 or dialysis
  - Time to doubling of creatinine
  - Time to > 40% reduction in eGFR
- Renal response and progression in patients with maintained hematologic responses at 26 months
- Safety and tolerability of NEOD001
- All cause mortality at 26 months

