#### **4.4 Early Termination from the Study**

Early termination occurs if the subject fails to complete the entire study, through the confirmatory EOS visit and 12-month period after the confirmatory EOS visit. Subjects may withdraw their consent to participate in this study at any time without prejudice. The Investigator must withdraw from the study any subject who requests to be withdrawn. A subject's participation in the study may be discontinued at any time at the discretion of the Investigator in accordance with his/her clinical judgment. The Sponsor (Tufts) or its designee should be notified in a timely manner of all subject discontinuations. When possible, the tests and evaluations listed for the ETD Visit should be carried out.

Early termination from the study may occur if:

- In the opinion of the Investigator, the subject cannot safely participate in the procedures required by the protocol
- Subject withdraws consent
- Subject is unwilling or unable to comply with the study requirements
- Subject is lost to follow-up

The Sponsor, (Tufts Medical Center) and the Prothena Therapeutics Limited who is funding the study reserve the right to discontinue the study at any time for any reason, including but not limited to, clinical or administrative reasons, or to discontinue participation of an individual Investigator or site for any reason, including but not limited to, poor enrollment or noncompliance. At any point in the study, if the subject is unwilling to return to the clinic for further visits but is willing to discuss their health status by phone, follow-up phone calls should be made to the subject or their caregiver every 3 months.

Vital status will be collected within legal and ethical boundaries for all randomized subjects receiving at least one dose of study drug and will be searched in public sources. During the study close-out period, at completion of the last subject's participation in the OLE, survival status will be collected within legal and ethical boundaries for all randomized subjects who withdrew participation from the main or OLE study. If vital status is determined, the subject will not be considered lost to follow-up.

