### Exclusion:

Subjects must **not meet any** of the following criteria:

1. Female patients who are lactating, breastfeeding, or pregnant. Men and women of childbearing potential need to use birth control while participating in the study.
2. Patients who did NOT complete the entire active study period of RAIN
3. Patients who are CKD 4 or 5 or on dialysis (eGFR  $< 30$ )

4. Medically documented cardiac syncope, uncompensated congestive heart failure, myocardial infarction within the previous 6 months, unstable angina pectoris, clinically significant repetitive atrial or ventricular arrhythmias despite antiarrhythmic treatment, or severe orthostatic hypotension or clinically significant uncompensated autonomic insufficiency.
5. Comorbid systemic illnesses or other severe concurrent disease which, in the judgment of the investigator, would make the patient inappropriate for entry into this study or interfere significantly with the proper assessment of safety and toxicity of the prescribed regimens.
6. Ongoing or active infection, known HIV positive, known to be hepatitis B surface antigen-positive or has known or suspected active hepatitis C infection.
7. Psychiatric illness/social situations that would limit compliance with study requirements

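### Scheduled vital-status calls end at month 24, but all-cause mortality is an endpoint at month 26, and section 4.4 closes the gap only in part

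*Combined protocol and SAP*

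**What the plan says.** Section 3.2.2 lists "All cause mortality at 26 months" as a secondary endpoint. The synopsis, section 1.1, section 2 and section 6.5.2.2 repeat it.

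Section 6.4 sets the call schedule: "Conduct vital status telephone call approximately 4 weeks after ETD visit or confirmatory EOS visit and approximately every 3 months thereafter", and this continues "until 24 months after study entry if the subject does not comply with standard-of-care visits or testing".

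Section 4.4 contains three further provisions:

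- A general rule: "Vital status will be collected within legal and ethical boundaries for all randomized subjects receiving at least one dose of study drug", with a search of public sources. No date is given.
- Three-monthly calls to the subject or caregiver when a subject will not return to clinic but will talk by phone. No end date is given.
- A close-out check, made when the last subject finishes the OLE: "survival status will be collected within legal and ethical boundaries for all randomized subjects who withdrew participation from the main or OLE study".

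Subjects in the OLE are seen monthly (section 3.6). The OLE exclusion list in Appendix 11 rules out anyone who did not complete the active study period, and also "Patients who are CKD 4 or 5 or on dialysis". Entry to the OLE is optional.

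**The concern.** The section dedicated to vital-status follow-up stops two months before the time point of the endpoint it serves. OLE participants have monthly visits, and subjects who keep attending standard-of-care visits are seen there. The people who depend on the 6.4 calls are the rest: outside the OLE and not attending.

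That group is selected. The OLE excludes subjects whose kidney function has fallen to CKD 4 or 5. It also excludes those who left the active period, and section 8.5 plans for 18% drop-out from hematologic progression requiring chemotherapy. Missing status among such subjects is unlikely to be unrelated to prognosis.

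The analysis text does not deal with the gap. Section 8.3.2 names no method or censoring rule for mortality, and section 8.6 rules out imputation. A subject last known alive at month 22 therefore has no defined status at month 26.

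**Working it through.** **1. Where 26 months comes from.** The synopsis states: "Each subject's study duration may be up to 26 months, consisting of a Screening Phase (1 month), a Treatment and Assessment Phase (13 months"), followed by a 12-month OLE. 1 + 13 + 12 = 26, so the plan's figure reproduces.

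**2. Whether the clocks differ.** Section 6.4 counts from study entry. Section 1.1 uses the same origin for the companion renal endpoint ("rates of renal response and progression at 26 months after study entry") and names 26-month mortality in the next sentence without another origin. On a common clock the call window ends 26 − 24 = 2 months early.

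**3. When the last call falls.** One month is taken as 365.25/12 = 30.44 days. The first call is 28 days after the early-discontinuation (ETD) or confirmatory end-of-study (EOS) visit, and later calls follow every 3 months, cut at month 24.

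Example with 28-day cycles and entry at first dose: the confirmatory EOS visit is at day 11 × 28 + 30 + 30 = 368. The first call is at day 396, and 396/30.44 = month 13.0. Further calls fall at months 16.0, 19.0 and 22.0. The next would be at month 25.0, which is outside the window.

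Study entry is not defined, so each case was run with entry at first dose and with entry 28 days earlier.

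| Starting point | Entry at first dose: last call (gap to month 26) | Entry 28 days earlier: last call (gap to month 26) |
|---|---|---|
| Confirmatory EOS, 28-day cycles | 22.0 (4.0) | 22.9 (3.1) |
| Confirmatory EOS at nominal month 13 | 22.9 (3.1) | 23.8 (2.2) |
| ETD after 1 dose | 22.9 (3.1) | 23.8 (2.2) |
| ETD after 6 doses | 21.5 (4.5) | 22.4 (3.6) |

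The last call lies at month 21.5 to 23.8, and the gap to month 26 is 2.2 to 4.5 months.

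**4. Whether changing the number is enough.** If 24 became 26 on the same three-monthly grid, each subject would gain at most one call, at about month 24.5 to 25.9, and in two of the eight cases none. The first grid call at or after month 26 would fall at month 26.8 to 28.9. A contact tied to month 26 is needed.

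**5. Size.** The documents give no mortality rate, so constant annual mortality a of 3% to 15% is assumed. Then S(t) = (1 − a)^(t/12), and the share of deaths in the last two months is [S(24) − S(26)] / [1 − S(26)].

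| a | S(24) | S(26) | Deaths in months 24–26 per 100 call-dependent subjects | Share of deaths by month 26 |
|---|---|---|---|---|
| 3% | 0.9409 | 0.9361 | 0.48 | 7.5% |
| 5% | 0.9025 | 0.8948 | 0.77 | 7.3% |
| 10% | 0.8100 | 0.7959 | 1.41 | 6.9% |
| 15% | 0.7225 | 0.7032 | 1.93 | 6.5% |

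Counted from a last call at month 22 instead, the figures are 1.0 to 3.9 per 100 and 13% to 15%. All of them apply only to subjects whose status rests on the 6.4 calls.

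**6. Scale in the trial.** If 5 to 10 of the 100 subjects were in that position and were not found by any other route (an assumption), the expected number of missed deaths in months 24 to 26 is between 5 × 0.0048 = 0.02 and 10 × 0.0193 = 0.19.

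**The case against.** A reader might infer that subjects out of contact are simply not followed to the endpoint. Section 4.4 does not support that. Its general rule covers every randomized, dosed subject, including completers who cannot enter the OLE, and it has no 24-month limit. Its calls for subjects unwilling to attend are open-ended. A death before month 26 can also be established later, so a live call at month 26 is not the only route. This objection stands, and it reduces the point to incomplete and unaligned follow-up.

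It does not remove the point. The public-source search has no date and no named source. The open-ended calls in 4.4 overlap with the 24-month limit in 6.4, and a site following the dedicated section would stop at 24. The close-out check names only subjects who withdrew. Section 4.4 defines early termination broadly, so a completer who later drops out of contact might be counted there, but whether that amounts to withdrawing participation is unclear. Close-out is also tied to the last OLE participant, so a late-enrolled subject outside the OLE could be checked before month 26.

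A reader might also take 0.5 to 1.9 deaths per 100 as the loss in this 100-subject trial. That is the wrong denominator, as step 6 shows. Nor do the documents say that subjects with CKD 4 or 5 lose contact: those who keep attending standard care do not need the calls.

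Finally, if the 26 were counted in 28-day study months, it would be 26 × 28 = 728 days, or 23.9 calendar months, close to the 24 in 6.4. The documents do not state two clocks. Even on that reading, the latest last call (month 23.8) precedes the endpoint.

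**Conclusion.** The mismatch is real: the 6.4 calls end at month 24, in practice at month 21.5 to 23.8, and the mortality endpoint is at month 26. For subjects outside the OLE who do not attend standard-of-care visits, no scheduled 6.4 contact reaches the endpoint. Section 4.4 would recover some of their late deaths, but as written it does not ensure that it recovers all.

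Under an assumed constant annual mortality of 3% to 15%, about 6.5% to 7.5% of deaths by month 26 in that subset fall in months 24 to 26. The number for the whole trial is likely well below one death; it rests on an assumed subset of 5 to 10 subjects. No between-arm mortality test is specified, and the primary analysis and sample size do not change. This is a modest completeness problem in one secondary endpoint, worth correcting because the correction is simple.

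**What to change.** - **Section 6.4:** change 24 months to 26 months after study entry, and add a final contact at or after month 26. The new number alone is not enough on a three-monthly grid.
- **Section 4.4:** apply both the vital-status search and the close-out survival check to every randomized, dosed subject not followed in the OLE, whether or not they withdrew, timed at or after that subject's own month 26.
- **Both sections:** state the origin (first dose or start of screening) and use it for the calls and for the endpoint.

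The cost is one or two extra calls or record checks per affected subject, and edits to two sections.
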